IL-7R is the top gene identified in synovial fluid macrophages and its expression in monocytes ( $R^2=0.56$  and  $p=8.4x10^{-5}$ ) and macrophages ( $R^2=0.56$  and  $p=2.4x10^{-6}$ ) strongly correlates with RA disease activity suggesting that IL-7R may be a predictor for disease severity. Hence in this proposal, novel translational studies will be performed in order to determine whether IL-7R and IL-7 are RA signature genes for disease activity and if these genes are markedly reduced in anti-TNF- $\alpha$  therapy responders compared to nonresponders.

**Figure 1.** Specific aim is proposed to elucidate the significance of IL-7/IL-7R expression in peripheral blood cells to RA disease activity and response to anti-TNF- $\alpha$  treatment.

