#### 2. Protocol Methodology

**Detection of IL-7 and IL-7R expression levels in RA patients with active and inactive disease:** RA patients will be referred and informed written consent will be obtained by [name]. Blood samples will be collected from patients that have been diagnosed with RA based on ACR classification criteria. The study will include 200 donors. The total number of subjects are divided into two groups to yield a power of 95% at a type I error 5% level [determined based on the preliminary data]. In the first group, 200 donors will be treated with methotrexate, plaquenil and/or prednisone (DMARDs) that either achieve remission (DAS28<2.6) or do not achieve remission (DAS28<2.6). 50 donor will be utilized as they respond to DMARDs and achieve remission (DAS28<2.6) and 150 donors that do not respond to DMARDs will be transferred to second group. In the second group, 150 donors will be treated with methotrexate, plaquenil and/or prednisone and Cimzia® (provided to us by UCB).

In the first group of patients, blood samples will be obtained from RA patients treated with Disease modifying anti rheumatic drugs (DMARDs) such as methotrexate, plaquenil and/or prednisone that achieve remission (DAS28<2.6). The patients that achieve remission (DAS28<2.6), blood will only be taken once at the patients routine visit.

The second group will consist of RA patients that did not respond to "DMARDs". These patients will further receive (DMARDs) such as methotrexate, plaquenil and/or prednisone as well as Cimzia® (provided to us by UCB) free of charge. Cimzia® is a FDA approved drug and is a standard of care. Blood samples will be obtained from the patients treated with DMARDs including methotrexate, plaquenil, and/or prednisone and Cimzia® (provided to us by UCB) that have inactive remission (DAS28<2.6). In this group, blood samples will be collected onset of the study as well as 3 and 6 months after treatment with Cimzia at patient's visit through our collaboration with the aforementioned rheumatologists. Patients receiving intra-articular steroid injections will be excluded from the study.

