PB mononuclear cells will be isolated from RA whole blood and drawn into EDTA or CPT tubes and isolated by Histopaque gradient centrifugation. Monocytes will be isolated from RA PB mononuclear cells by negative selection (as shown in the preliminary data) and half of the monocytes will be differentiated to macrophages for 7 days. The expression levels for IL-7 and IL-7R will be determined by real-time RT-PCR and FACS analysis.

In our statistical analysis, we will first perform a stratified analysis to evaluate the differential expression levels in RA patients with active and inactive disease, controlling for the type of treatment. Data analysis will be performed in collaboration with an UIC Center for Clinical and Translational Science statistician. Specifically, we will perform the comparison of IL-7 and IL-7R expression among RA patients with active (DAS28>2.6) vs. inactive disease (DAS28<2.6) for DMARDs group (group 1). We will then perform a similar comparison for the DMARDs and Cimzia® therapy group (group 2). The stratified analysis can adjust for the potential confounding effect of treatment received and allows for the detection of the potential differential relationships between expression levels of IL-7 or IL-7R and disease status. We will also perform a pooled regression analysis in which the expression logarithm of IL-7 or IL-7R from patients is regressed on the treatment group indicator [DMARDs (group 1) versus on DMARDs plus Cimzia® therapy (group 2)] and disease status (active or inactive disease) which would demonstrate the interaction between treatment groups and disease activity. Such an analysis pools subjects from two treatment groups together and can therefore increase the sample size, and hence potentially the power of detecting the relationships between biomarkers and disease status. The RA samples will be collected over a 2 year period and the data will be analyzed in the last year of the proposal.

**Measure outcomes:** For any of the genes that demonstrate at least 2.5 fold increase (89% sensitivity calculated based on our preliminary data) in active disease compared to remission, correlation coefficient will be calculated for that gene expression level, rheumatoid factor, Cyclic Citrullinated Peptide Antibody (anti-CCP), C-Reactive Protein (CRP), DAS28 and disease duration.

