## 9. Type and Number of Experimental Subjects

Subjects include patients over age 18, excluding pregnant women (self-reported), with an RA diagnosis, or other autoimmune disease to be used as a control. 200 donors will be treated with methotrexate, plaquenil and/or prednisone (DMARDs) that either achieve remission (DAS28<2.6) or do not achieve remission (DAS28>2.6). 50 donor will be utilized as they respond to DMARDs and achieve remission (DAS28<2.6) and 150 donors that do not respond to DMARDs will be treated with DMARDs such as methotrexate, plaquenil and/or prednisone and Cimzia provided to us by UCB. Subjects that fulfill the eligibility criteria will be identified by their physician/rheumatologist to be consented in participating in the study.

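### Section 2 contradicts itself and the planned analyses on whose blood is taken in group 2; if the remission condition is applied at 3 and 6 months, no on-treatment sample comes from a patient still active on Cimzia

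*Combined protocol and SAP*

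**What the plan says.** **Whose blood is taken.** Section 2 (Protocol Methodology) obtains group 2 samples from patients on DMARDs plus Cimzia "that have inactive remission (DAS28<2.6"). The following sentence reads "In this group, blood samples will be collected onset of the study as well as 3 and 6 months after treatment with Cimzia" and attaches no DAS28 condition. The same paragraph defines group 2 as patients in whom DMARDs did not work. Section 9 describes that state as those who "do not achieve remission (DAS28>2.6"). For group 1, Section 2 describes blood only from remitters: "The patients that achieve remission (DAS28<2.6), blood will only be taken once at the patients routine visit".

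**What the samples are for.** The analysis text in Section 2 plans a comparison of "active (DAS28>2.6) vs. inactive disease (DAS28<2.6) for DMARDs group (group 1"), and continues: "We will then perform a similar comparison for the DMARDs and Cimzia® therapy group (group 2"). It adds a pooled regression of log expression on treatment group and disease status, meant to show their interaction. Aim 1 names active and inactive disease under both treatments. Section 1 asks whether the genes are lower in anti-TNF "therapy responders compared to nonresponders".

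**The concern.** The first sentence on group 2 sampling selects on the state that the analysis is meant to compare. A site that follows it could properly skip the 3- and 6-month draws in any patient whose DAS28 is above 2.6. Those patients are one side of the group 2 comparison and are the anti-TNF nonresponders of Section 1. Before-and-after change would then be seen only in patients who did well, and could not describe the treated group. The correlation analysis is also exposed, because it is triggered by expression being at least 2.5 times as high in active disease as in remission. A draw that is not taken cannot be recovered later.

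**Working it through.** **The plan's own power figures.** They do not bear on who is sampled.
- Section 10 gives 80% power for a paired t test with 200 subjects at effect size 1.25. The noncentrality is 1.25 × √200 = 17.7, so power is about 100% at two-sided 5%. An effect of about 0.20 is what gives 80% power with 200 pairs. The figure does not reproduce; that is a separate matter.
- Section 2 gives 95% power without an effect size or SD, so it cannot be checked.

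**Step 1: set the statements side by side.**

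| Place | Group 2 patients called for |
|---|---|
| Section 2, sampling, first sentence | DAS28<2.6 |
| Section 2, sampling, next sentence | the group, at onset, 3 and 6 months, no DAS28 condition |
| Section 2, group definition, with Section 9 | DMARD failures, DAS28>2.6 at entry |
| Aim 1 | active and inactive |
| Section 2, analysis | active and inactive |
| Section 1 | anti-TNF responders and nonresponders |

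The first row conflicts with every other row. No other section lifts the condition: Section 9 repeats the group sizes but does not say when group 2 blood is drawn.

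**Step 2: what each draw supplies if the condition is applied at follow-up.** I assume that the onset draw precedes the first Cimzia dose.
- Onset: patients with active disease, including those who will later fail Cimzia, since response is not yet known.
- 3 and 6 months: remitters contribute; patients still active contribute 0.

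If a share r of the 150 is in remission at a visit, 150 × (1 − r) samples are not drawn at that visit. That is 135 at r = 10% and 75 at r = 50%. The documents give no remission share, so r is an assumption. The empty active cell does not depend on it.

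**Step 3: the four cells of the pooled regression under that reading.** The plan does not say how onset samples are labelled.
- Labelled as group 2: the DMARD-alone active cell is empty, because group 1 sampling is described only for remitters. The group 2 active cell holds only pre-Cimzia blood.
- Labelled as group 1: the group 2 active cell is empty.

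Either way there are three cell means for four parameters (intercept, group, status, interaction), so the interaction is not estimable.

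**Step 4: what is recovered if all 150 are sampled.** This takes one sample per patient at one visit, a two-sample t test and two-sided alpha 0.05. The detectable standardised difference is approximately (z₀.₉₇₅ + z_power) × √(1/n₁ + 1/n₂). For 30 v 120 at 80% power: 2.80 × √(1/30 + 1/120) = 2.80 × 0.204 = 0.57. The noncentral t gives 0.58. Noncentral t results:

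| Remission share (assumed) | Inactive v active | 80% power | 95% power |
|---|---|---|---|
| 10% | 15 v 135 | 0.77 | 0.99 |
| 20% | 30 v 120 | 0.58 | 0.74 |
| 30% | 45 v 105 | 0.50 | 0.65 |
| 40% | 60 v 90 | 0.47 | 0.60 |
| 50% | 75 v 75 | 0.46 | 0.59 |

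**The case against.** The best defence is that the remission phrase is a drafting slip. The state it names is not defined anywhere. Earlier in Section 2 the text prints DAS28<2.6 for patients who do not reach remission, which Section 9 prints as >2.6. Aim 1, Section 1 and the analysis text all call for both disease states. The weight of the text is therefore against a deliberate restriction. That argument stands as far as intent goes, and it makes this an internal contradiction more than a chosen design. It does not remove the problem. Section 9 corrects the other sign but is silent on group 2 sampling, and nothing else tells a site to draw follow-up blood from patients who remain active.

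A reader might go further and infer that Cimzia nonresponders are never sampled, or that the study holds no blood from active disease. The documents do not support that. The group 2 sentence does not say remitters only. The scheduled onset draw falls before response is known, in patients who entered with active disease. Later nonresponders should therefore have a pre-Cimzia sample, and baseline expression could be compared by later response. That addresses prediction, however, and not whether expression falls more in responders.

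Nor can one say outright that the effect of Cimzia will be overstated. That depends on follow-up draws actually being limited to remitters, which the text leaves unsettled.

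**Conclusion.** The contradiction is real and must be resolved before follow-up sampling. If the remission condition is applied at 3 and 6 months, the on-treatment active cell in group 2 is 0. The group 2 active-versus-inactive contrast on treatment, and the change in responders versus nonresponders, then cannot be estimated. This follows from the wording and needs no assumed remission share. It does rest on the restrictive reading being followed, which the documents neither confirm nor exclude. Active-disease samples at onset survive on the schedule as written, but the plan gives them no role in the analysis.

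**What to change.** **Sampling text, Section 2.** Delete the remission condition from the group 2 sentence. State that all 150 group 2 donors give blood at onset, 3 and 6 months whatever their DAS28, and that DAS28 is recorded at each draw.

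**Analysis text, Section 2.**
- Define onset samples as pre-Cimzia. Say whether they serve as baseline for change or as the DMARD-alone active samples that group 1 lacks.
- Use only the 3- and 6-month samples, classified by DAS28 at that draw, for the group 2 active-versus-inactive comparison. Classifying every draw this way would put pre-Cimzia blood into the Cimzia stratum and confuse disease status with time on treatment.
- Account for repeated draws from the same patient, for example with a mixed model or by naming one follow-up visit as the main one. The regression is described without repeated measures. If onset samples stand in for group 1, the same patients appear in both strata, and the model must allow for that too.

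**Cost.** Some rewording in two places and some extra analysis work. The visits and draws are already planned, so no new patient contact is needed.

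### Group 1 has no active patients, so its active-versus-inactive comparison cannot be run, the group-by-activity interaction is not identified, and no product term is listed

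*Combined protocol and SAP*

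**What the plan says.** All references are to the combined protocol and SAP.

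- **Group membership (Section 2).** The first group opens with 200 DMARD-treated donors, some of whom reach remission and some of whom do not. The 50 remitters are kept, and "150 donors that do not respond to DMARDs will be transferred to second group". Section 9 gives the same 50/150 split without naming groups: "150 donors that do not respond to DMARDs will be treated with DMARDs such as methotrexate, plaquenil and/or prednisone and Cimzia".
- **Sampling (Section 2).** Group 1 blood comes from remitters only: "The patients that achieve remission (DAS28<2.6), blood will only be taken once at the patients routine visit". For group 2, "blood samples will be collected onset of the study as well as 3 and 6 months after treatment with Cimzia". Another sentence in that paragraph describes the group 2 samples as coming from patients "that have inactive remission (DAS28<2.6").
- **Analysis (Section 2).** The first analysis is stratified: "active (DAS28>2.6) vs. inactive disease (DAS28<2.6) for DMARDs group (group 1"), then the same contrast in group 2. A pooled regression of log expression follows, on a group indicator and "disease status (active or inactive disease) which would demonstrate the interaction between treatment groups and disease activity". Its stated advantage is this: "Such an analysis pools subjects from two treatment groups together and can therefore increase the sample size".

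**The concern.** Allocation to the two groups is decided by disease status on DMARDs, yet the analysis treats disease status as something that varies within each group. If every non-remitter leaves group 1, the DMARD-only half of Aim 1 has no active arm. The interaction asks whether the activity difference is the same in both groups, and it needs that difference to exist in both.

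An analyst could rescue the comparison only by deciding, with the data in hand, which samples count as active on DMARDs alone and whether repeated samples from one patient are treated as independent. Both decisions affect the result and belong in the plan.

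**Working it through.** **Inputs.** 200 donors, 50 remitters kept, 150 non-responders transferred (Section 2; split repeated in Section 9). One draw per group 1 patient; three draws (onset, 3 and 6 months) per group 2 patient. The plan gives no figure for this analysis that could be reproduced.

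**1. Cell count.** Group 1 active = 200 − 150 − 50 = 0. Group 1 inactive = 50.

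**2. Interaction.** Let G = 1 for group 2 and A = 1 for active disease. The cells that can occur are:

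| Cell | Intercept | G | A | G×A |
|---|---|---|---|---|
| Group 1, inactive | 1 | 0 | 0 | 0 |
| Group 2, active | 1 | 1 | 1 | 1 |
| Group 2, inactive | 1 | 1 | 0 | 0 |

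The A and G×A columns are identical, so the rank is 3 of 4. Writing in the product term does not help while the group 1 active cell is empty.

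**3. Main-effects model.** Three parameters fit three cell means exactly:

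- A coefficient = group 2 active mean − group 2 inactive mean
- G coefficient = group 2 inactive mean − group 1 inactive mean

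A numerical check with group 2 split 75/75 (assumed) gave 1.074 for A and 0.413 for G, each equal to the corresponding difference in means. Group 1 therefore adds nothing to the activity estimate except through the residual variance.

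**4. Other readings.**

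| Reading | Model | Rank |
|---|---|---|
| Group coding, group 2 onset samples only (all active) | main effects | 2 of 3 |
| Group coding, group 2 samples all in remission | main effects | 2 of 3 |
| Strata by treatment at the draw | with product term | 4 of 4 |
| Strata by treatment at the draw, Cimzia draws in remission only | with product term | 3 of 4 |

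**5. If the onset samples fill the cell.** The same 150 patients then supply both treatment levels. I simulated a true null with 50 single samples plus 150 patients × 3 draws, onset all active. Assumptions: within-patient correlation 0.3, 0.5 or 0.7; remission on Cimzia 30% or 50%. Persistence of status from 3 to 6 months is expressed as a latent correlation. There were 4,000 runs per setting (Monte Carlo error about ±0.7 points). Type I error of ordinary regression at a nominal 5%:

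| Latent status correlation | Interaction | Pooled status effect |
|---|---|---|
| 0 | 5.0–6.0% | 4.4–5.2% |
| 0.5 | 4.9–6.1% | 5.1–6.7% |
| 0.99 | 5.8–7.9% | 7.0–10.0% |

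A separate simulation reached upper ends of 8.7% and 11.2%. Generalised least squares with the true within-patient correlation, standing in for a mixed model, gave 4.3–5.4% and 4.1–5.5%.

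**6. Value of pooling on that reading.** Under a common status effect, the SD of the estimate (in SD units of log expression) is 0.09–0.12 pooled by ordinary regression, against 0.16–0.17 for DMARD-only and 0.12–0.16 for Cimzia. So pooling can gain precision, but only once the empty cell is filled, and with no patients beyond the 200.

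**The case against.** - **Group 1 starts with all 200 donors.** Section 2 does place remitters and non-remitters there at first, and Aim 1's wording fits strata by treatment at the draw. This shows that the text is inconsistent. It does not supply an active group 1 sample: the 150 are transferred out, and group 1 blood is limited to remitters.
- **The onset draw is naturally a baseline sample.** It is contrasted with draws 3 and 6 months after Cimzia, and the paired t tests in Section 10 suggest before-and-after thinking. This is probably right, and it means the data needed for a repair are likely in the design. But the onset draw is listed under group 2, and the regression codes treatment by group, so an analyst following the plan would code those samples as DMARDs plus Cimzia.
- **The remission sentence for group 2 looks like a slip.** Probably so. The same section prints DAS28<2.6 for patients who do not reach remission, where Section 9 prints DAS28>2.6. It is a point to reconcile and does not carry the finding.
- **The product term is implied.** The intent to study an interaction is clear, but the listed terms do not deliver it, and adding one would not be enough.
- **The type I error inflation is mostly small.** This stands. It is close to nominal unless status is very persistent, and the use of ordinary regression on all draws is an assumption, since the plan does not say which draws enter.

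**Conclusion.** The concern holds. Under the groups as defined, the group 1 comparison has 0 active patients and the interaction model has rank 3 of 4. Both results follow from the plan's own counts and need no assumption about effect size or variance. The main-effects model can be fitted if group 2 includes both active and inactive samples, but its activity coefficient is then the group 2 difference alone.

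The type I error figures are secondary. They apply only if the onset samples fill the empty cell and within-patient correlation is ignored, and they rest on assumed correlations, remission rates and persistence of status, none of which the documents give.

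This must be fixed before analysis: the first analysis described cannot be carried out as written for one of its two strata.

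**What to change.** 1. In the statistical analysis part of Section 2, define strata by treatment at the time of the draw. DMARD-only: the 50 remission samples against the group 2 onset samples. DMARDs plus Cimzia: the 3- and 6-month samples, active against inactive.
2. In the sampling part of Section 2, state that the onset draw precedes the first Cimzia dose, if that is the case. If it is not, drop the group 1 comparison and the interaction.
3. Fit a linear mixed model of log expression on treatment at the draw, disease status and their product, with a random patient intercept. Another method that allows for within-patient correlation would also serve, if named in advance.
4. Reconcile the sentence describing group 2 samples as in remission with the planned active-versus-inactive comparison. Reconcile the DAS28 sign for non-remitters in Section 2 with Section 9.
5. Reword the pooling claim: the gain is in samples and in precision under a common status effect, not in patients.
6. State as a limitation that activity in the DMARD-only stratum is fully tied to DMARD response and that the 50 remitters never receive Cimzia. The mixed model corrects standard errors, not this confounding.

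The cost is rewording in Section 2 and slightly more analysis work, with no new draws if the onset sample precedes Cimzia. The claim about the interaction becomes more cautious.

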#### 1. Background and Purpose

Monocyte migration plays a key role in the pathogenesis of Rheumatoid arthritis (RA) since the number of monocyte derived macrophages is higher in RA synovial tissue compared to normal joints and is well correlated with radiological damage, joint pain and inflammation. However, the signaling pathway(s) responsible for enhanced recruitment of monocytes into the RA synovial joint space is unknown. To address this important issue, we performed microarray studies to identify differentially regulated genes in RA synovial fluid macrophages and identified IL-7 Receptor (IL-7R) as one of the most highly upregulated genes in RA synovial fluid macrophages. Our preliminary data shows that IL-7R expression is elevated 45 fold in RA synovial fluid and 10 fold in RA peripheral blood (PB) in vitro differentiated macrophages compared to normal PB macrophages by real-time RT-PCR and/or FACS analysis. Consistently, in RA synovial tissue, IL-7R is also elevated on macrophages in the lining and sublining compared to normal synovial tissue. We found that expression of IL-7R in RA PB monocytes and macrophages is modulated by TNF- $\alpha$  Interestingly, concentrations of IL-7R have a strong correlation with disease activity score as determined by 28 joint count (DAS28) and TNF-α levels in RA monocytes. Moreover, our preliminary data documents that IL-7 is secreted from TNF-a treated RA macrophages and can attract IL-7R+ monocytes from the circulation to the RA joint at concentrations of IL-7 detected in RA synovial fluid.

Based on our results we hypothesize that RA patients with a TNF- $\alpha$  driven active disease have elevated expression of IL-7/IL-7R and thereby response to anti-TNF- $\alpha$  therapy reduces IL-7-mediated monocyte migration and the number of IL-7R+macrophages in the RA joint. To test our hypotheses, in aim 1 we will examine whether expression of IL-7 or IL-7R in RA PB cells correlates with RA disease severity and response to anti-TNF- $\alpha$  treatment (Fig. 1). To date the contribution of IL-7 and IL-7R to RA pathogenesis and its role as a TNF- $\alpha$  responsive gene has not been described.

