#### To accomplish the proposed project we will:

**Aim 1.** Determine whether the levels of IL-7 and IL-7R are elevated in PB mononuclear cells, PB monocytes or differentiated PB macrophages of RA patients with active [disease activity score (DAS)28>2.6] and inactive disease (DAS28<2.6) treated with Disease modifying anti rheumatic drugs (DMARDs) alone and/or DMARDs plus Cimzia® (certolizumab Pegol).

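### Group 2 is sampled before and after Cimzia, but no responder-versus-nonresponder comparison of change from onset is specified, and the planned level comparison names no visit

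*Combined protocol and SAP*

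**What the plan says.** Section 1 (Background and Purpose) sets two tasks. One is association: "we will examine whether expression of IL-7 or IL-7R in RA PB cells correlates with RA disease severity and response to anti-TNF" treatment. The other asks "if these genes are markedly reduced in anti-TNF" "therapy responders compared to nonresponders". The hypothesis in the same section is that responding to the drug lowers IL-7-driven monocyte migration. Aim 1 is worded in levels: "Determine whether the levels of IL-7 and IL-7R are elevated in PB mononuclear cells" and related cell types, by active or inactive disease.

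Section 2 (Protocol Methodology) gives the sampling. For the Cimzia group: "In this group, blood samples will be collected onset of the study as well as 3 and 6 months after treatment with Cimzia". For the DMARD remitters: "50 donor will be utilized as they respond to DMARDs and achieve remission (DAS28<2.6)", and for them "blood will only be taken once at the patients routine visit".

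The analysis part of Section 2 compares expression by active versus inactive status in group 1, and then: "We will then perform a similar comparison for the DMARDs and Cimzia" group. It adds a pooled regression of log expression on treatment group and disease status, and correlations of expression level with clinical measures. Section 10 states the power of a paired t test on 200 subjects and does not say what is paired.

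**The concern.** The question of reduction in responders needs three things: a before value, an after value, and a contrast between responders and nonresponders. The design collects the first two. No stated analysis makes the contrast on change.

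The visit matters as well. Group 2 is made up of patients who did not reach remission on DMARDs, so at onset it should hold almost no inactive patients. Its active-versus-inactive comparison therefore has to use follow-up samples. The text does not say whether these are the 3-month samples, the 6-month samples or all of them. Pooling visits would put up to three correlated samples per patient into a comparison with no term for that.

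At stake is the interpretation. Section 1 reports R² = 0.56 between IL-7R and disease activity. If patients who start nearer to DAS28 2.6 reach it more easily, they may already have had lower IL-7R before the first dose. A 6-month level difference could then be read as a reduction when nothing had fallen.

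**Working it through.** **1. Analyses set against the question**

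| Planned analysis | Outcome | Onset or visit term | Responder contrast on change |
|---|---|---|---|
| Group 2 active vs inactive (Section 2) | level | none, visit unnamed | no |
| Pooled regression (Section 2) | log level | none | no |
| Correlations (Section 2) | level | none | no |
| Paired t test (Section 10) | difference, pair undefined | possibly onset vs follow-up | no: mean change in one group |

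**2. The stated power and the number of pairs**

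Section 10 claims 80% power with 200 subjects at effect size 1.25. Read as mean difference over SD of differences, the noncentrality is 1.25 × √200 = 17.7, and power exceeds 99.99%. Power of 80% needs only 8 pairs two-sided (78.6% with 7, 85.6% with 8). The figure is not reproduced. That is a separate defect, and this point does not rest on it.

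Onset-to-follow-up pairs: 200 − 50 remitters sampled once = at most 150. The paired effect detectable at 80% power is 0.20 SD with 200 pairs and 0.23 SD with 150.

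**3. Why a level comparison cannot isolate reduction**

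Level gap at follow-up = gap at onset + difference in change. If expression does not change, the level gap equals the onset gap.

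**4. Could an onset gap arise?**

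The documents give no group 2 inputs, so all of these are assumed:
- 150 patients; onset DAS28 mean 5 and above 2.6, SD s = 1 or 0.6.
- 6-month change mean −1.8, SD 1.2; correlation ρ between change and onset DAS28.
- Expression reliability 0.8, with no change in expression.
- Correlation r of expression with onset DAS28 of 0.3, 0.5 or 0.75 (0.75 = √0.56).

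The sign and strength of the onset gap follow cov(onset, 6-month DAS28) = s² + 1.2ρs.

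| s | ρ | s² + 1.2ρs | Level test rejects, r = 0.3 / 0.5 / 0.75 |
|---|---|---|---|
| 1 | 0 | 1.00 | 41 / 85 / 99.7% |
| 1 | −0.3 | 0.64 | 26 / 61 / 93% |
| 1 | −0.5 | 0.40 | 17 / 34 / 68% |
| 1 | −0.6 | 0.28 | 12 / 23 / 43% |
| 1 | −0.7 | 0.16 | 7 / 11 / 22% |
| 0.6 | 0 | 0.36 | 24 / 56 / 90% |
| 0.6 | −0.3 | 0.144 | 9 / 16 / 29% |
| 0.6 | −0.5 | 0 | about 5% |
| 0.6 | −0.6 | −0.072 | 7 / 8 / 13% |
| 0.6 | −0.7 | −0.144 | 11 / 24 / 46% (gap reversed) |

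The percentages are simulated. Hand check of s = 1, ρ = 0, r = 0.5:
- 6-month mean 5 − 1.8 = 3.2; SD √(1 + 1.44) = 1.56.
- Share below 2.6: Φ(−0.6/1.56) = 35%.
- Onset gap: 0.5 × (1/1.56) × φ(0.384)/(0.35 × 0.65) = 0.52 SD. The simulation gives 0.50, because it excludes onset values below 2.6.
- z = 0.50 × √(150 × 0.35 × 0.65) = 2.92; Φ(2.92 − 1.96) = 83%, against 85% simulated.

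In the same settings a two-sample test of change from onset rejects in about 4% to 6%.

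**5. Limit of the change test**

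If expression simply tracks DAS28 at 25% or 50% of the cross-sectional slope (ρ from 0 to −0.5), the change test rejects in 12% to about 100%. It shows that expression change goes with disease status, not that Cimzia caused it.

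**The case against.** A reader might infer that no analysis of change from onset is planned at all. The documents do not support that. Section 10 names a paired t test, only group 2 is sampled repeatedly, and onset versus follow-up is a natural reading of the pair. What is missing is narrower: a comparison of change between responders and nonresponders.

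The Section 1 question can also mean lower in responders than in nonresponders. On that reading the group 2 level comparison answers it once a visit is named, and Aim 1 itself speaks of levels. This stands, so the level comparison should stay. The hypothesis in Section 1 does, however, speak of response lowering migration, and onset samples are collected, so the question of change is also live.

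DAS28 below 2.6 is not defined as response to Cimzia. Section 2 links response to remission only for DMARDs. This stands too, and the sponsor has to confirm the definition.

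The high rejection rates might be taken as the expected error rate. They are not. Every DAS28 input is assumed, and ρ = 0 makes the DAS28 SD grow from 1 to about 1.5. At a roughly constant SD (s = 1, ρ about −0.6) the rates are 12%, 23% and 43%. The null also holds expression fixed while DAS28 falls by 1.8.

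Finally, nothing in the plan says that a level difference will be reported as a reduction. The point is that the stated analyses could not tell the two apart.

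**Conclusion.** The concern holds in this limited form. The plan asks about reduction in responders and collects the samples to study it, but specifies no responder-versus-nonresponder comparison of change. The group 2 level comparison names no visit. The paired t test has no defined pair and at most 150 onset-to-follow-up pairs.

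These findings come from the text and need no assumptions. The size of any bias cannot be derived from the documents. Under the assumed inputs it runs from no excess (about 5%) to over 99% rejection, and the onset gap can even reverse. That shows the bias is possible and says nothing about its likely size. The change should be made because it is cheap and uses samples already planned.

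**What to change.** 1. Add to the analysis text of Section 2:

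> *In group 2, change in log expression from onset to [named visit] will be compared between patients with DAS28<2.6 and those with DAS28>2.6 at that visit by a two-sample test, and reported as an association of expression change with disease status, not as proof of a Cimzia effect.*

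The cut-off is the plan's own active/inactive threshold. The sponsor should confirm that it is what Section 1 means by a responder.

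2. Keep the active-versus-inactive level comparison for Aim 1, name its visit, and use one sample per patient.

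3. Define the pair in Section 10. If it is onset to follow-up, restate the number as at most 150.

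4. Reconcile the Section 2 sentence that describes the sampled Cimzia patients as being in remission with the active-versus-inactive comparison in the same group. Read literally, it leaves no active patients to compare.

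**Cost.** Wording only, with no new visits or samples. Patients without an onset sample, or without DAS28 at the named visit, drop out of the change comparison. With 150 patients and an assumed 30% below 2.6 (45 vs 105), the difference detectable at 80% power is about 2.80 × √(1/45 + 1/105) = 0.50 SD of change. It ranges from 0.77 to 0.46 SD for shares of 10% to 50%. Losing 25% of patients multiplies it by √(1/0.75) = 1.15, so 0.50 becomes about 0.58.

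The comparison also adds tests: 2 genes × up to 3 cell populations × 2 assays = up to 12. Name the main one, or label them all exploratory.
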